8.3.3 CLASSIFICATION OF AN ADVERSE EVENT

8.3.3.1 SEVERITY OF EVENT

The following guidelines will be used to describe AE severity.

- **Mild** – Events require minimal or no treatment and do not interfere with the participant’s daily activities.
- **Moderate** – Events result in a low level of inconvenience or concern with the therapeutic measures. Moderate events may cause some interference with functioning.
- **Severe** – Events interrupt a participant’s usual daily activity and may require systemic drug therapy or other treatment. Severe events are usually potentially life-threatening or incapacitating. Of note, the term “severe” does not necessarily equate to “serious.”

8.3.3.2 RELATIONSHIP TO STUDY INTERVENTION

All adverse events (AEs) must have their relationship to study intervention assessed by the clinician who examines and evaluates the participant based on temporal relationship and his/her clinical judgment. The degree of certainty about causality will be graded using the categories below. In a clinical trial, the study product must always be suspect.

- **Related** – The AE is known to occur with the study intervention, there is a reasonable possibility that the study intervention caused the AE, or there is a temporal relationship between the study intervention and event. Reasonable possibility means that there is evidence to suggest a causal relationship between the study intervention and the AE.
- **Not Related** – There is not a reasonable possibility that the administration of the study intervention caused the event, there is no temporal relationship between the study intervention and event onset, or an alternate etiology has been established.

8.3.3.3 EXPECTEDNESS

The treating physician will be responsible for determining whether an adverse event (AE) is expected or unexpected. An AE will be considered unexpected if the nature, severity, or frequency of the event is not consistent with the risk information previously described for the study intervention.

8.3.4 TIME PERIOD AND FREQUENCY FOR EVENT ASSESSMENT AND FOLLOW-UP

The occurrence of an adverse event (AE) or serious adverse event (SAE) may come to the attention of study personnel during study visits and interviews of a study participant presenting for medical care, or upon review by a study monitor.

All AEs including local and systemic reactions not meeting the criteria for SAEs will be captured on the adverse event form. Information to be collected includes event description, time of onset, clinician’s assessment of severity, relationship to study product (assessed only by those with the training and authority to make a diagnosis), and time of resolution/stabilization of the event. All AEs occurring while on study must be documented appropriately regardless of relationship. All AEs will be followed to adequate resolution.

Any medical condition that is present at the time that the participant is screened will be considered as baseline and not reported as an AE. However, if the study participant’s condition deteriorates at any time during the study, it will be recorded as an AE. AEs to anticipate are ocular in nature.

Changes in the severity of an AE will be documented to allow an assessment of the duration of the event at each level of severity to be performed. AEs characterized as intermittent require documentation of onset and duration of each episode.

The masked treating physician will record all reportable events with start dates occurring any time after informed consent is obtained until 7 (for non-serious AEs) or 30 days (for SAEs) after the last day of study participation. At each study visit,

DETECT

Version 5.0
21 March 2023

the investigator will inquire about the occurrence of AE/SAEs since the last visit. Events will be followed for outcome information until resolution or stabilization. Each AE is to be classified by the Investigator as SERIOUS (SAE) or NONSERIOUS (NSAE). If a SAE occurs during the study, the investigator at the enrollment site must fill out the serious adverse event form and email it to the Medical Monitor at UCSF, within 24 hours of the occurrence of the SAE and or when it was discovered. The AEs are recorded as they are presented from patients and or are discovered.

8.3.5 ADVERSE EVENT REPORTING

All AEs will be recorded in both the follow-up form and in a specific adverse event form.

8.3.6 SERIOUS ADVERSE EVENT REPORTING

All AEs should be followed until they are resolved or until a stable clinical endpoint is reached. Each AE is to be classified by the Investigator as SERIOUS (SAE) or NONSERIOUS (NSAE). If an SAE occurs, the investigator must complete the serious adverse event form in REDCap for review by the Medical Monitor at UCSF, [name], within 24 hours of the occurrence of the SAE. The investigator must provide written follow-up reports until the SAE or clinically significant AE has resolved or until a stable clinical endpoint is reached. Notification of an SAE or clinically significant AE must also be submitted to the Lead PI/Clinical Coordinating Center for submission to WCG IRB and Data and Safety Monitoring Committee (DSMC) in accordance with its requirements. Quarterly Serious Adverse Events summary reports will be sent to the Data and Safety Monitoring Committee (DSMC). All AEs must be reported from the time that the subject provides informed consent through the last study visit.

Clinical data (including adverse events (AEs), concomitant medications, and expected adverse reactions data) and clinical laboratory data will be entered into Research Electronic Data Capture (REDCap), a 21 CFR Part 11-compliant data capture system provided by the Data Coordinating Center at UCSF.

The study sponsor will be responsible for notifying the Food and Drug Administration (FDA) of any unexpected fatal or life-threatening suspected adverse reaction as soon as possible, but in no case later than 7 calendar days after the sponsor's initial receipt of the information.

8.3.7 REPORTING EVENTS TO PARTICIPANTS

AEs and SAEs will be discussed on an individual level with the masked treating physician. At the end of the study, all study participants will be given a report of the results in their native language.

8.3.8 EVENTS OF SPECIAL INTEREST

Not applicable.

8.3.9 REPORTING OF PREGNANCY

Women of childbearing age (ie women who have been told by their doctors that they need to take birth control to avoid pregnancy) will be required to take a urine test prior to enrolling in the study. Women of childbearing age will need to use birth control while taking Ripasudil. Women will check with their doctor about what kind of birth control methods to use and how long to use them. For this study women of childbearing age would only need to use birth control for the three months of taking Ripasudil.

There is no available data on the risk of taking Ripasudil during pregnancy; however, the systemic absorption from a topical eye drop is low. If a participant gets pregnant while taking the study drug, they will stop taking the study drug. Participants will continue in study and we will follow the patient until the end of the study- regardless of their ability to continue the study drug.

DETECT

Version 5.0
21 March 2023

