160 participants with moderate to severe Fuchs (DETECT I) and 60 participants with mild Fuchs (DETECT II) will be enrolled at Oregon Health & Science University, Stanford University, University of Pennsylvania, University of California Davis, and at Dartmouth-Hitchcock Medical Center. We anticipate participants from each enrollment site will match the demographic makeup of the city the site is located in. Therefore, our study population will be mostly White (non-Hispanic), Hispanic, African-American, and Asian based on the most recent census data for each enrollment area. There is evidence that endothelial dystrophy is more common in women, and the previous DETECT-Therapeutic Exploratory Study (TES) enrolled 58% women. We anticipate a similar gender makeup in this study. In the DETECT-TES the median age of study participants was 67, with an interquartile range of 64 to 71; we expect a similar age range in this study.

Phase:

N/A

Description of Sites/Facilities Enrolling Participants:

Participants will be enrolled at five sites in the United States: Oregon Health & Science University (Portland, OR), Stanford University (Palo Alto, CA), University of Pennsylvania (Philadelphia, PA), University of California Davis (Davis, CA), and Dartmouth-Hitchcock Medical Center (Lebanon, NH). Patients will be enrolled at the Cornea Clinic in each hospital.

DETECT

Version 5.0
21 March 2023**Description of Study
Intervention:****DETECT I**

Study participants will all undergo endothelial keratoplasty followed by an adjuvant topical medication post-operatively. Participants will be randomized to one of four treatment groups in this 2x2 factorial design study:

		Endothelial Keratoplasty	
		UT-DSAEK	DMEK
Adjuvant Topical Medication	Ripasudil 0.4%	UT-DSAEK + 0.4% ripasudil	DMEK + 0.4% ripasudil
	Placebo	UT-DSAEK + placebo	DMEK + placebo

All patients will be randomized to undergo one of two types of endothelial keratoplasty. All patients will be randomized to receive either topical ripasudil 0.4% or topical placebo. Patients will begin topical medicines post-op day 1. They will take their assigned study medication 4x/day for 3 months.

DETECT II

[figure not shown]
[figure not shown]
[figure not shown]
[figure not shown]
[figure not shown]
[figure not shown]

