5 STUDY POPULATION

5.1 INCLUSION CRITERIA

In order to be eligible to participate, an individual must meet all of the following criteria:

DETECT I

- Dysfunctional endothelium from Fuchs Endothelial Corneal Dystrophy (FECD) with guttata extending beyond 4.5 mm of the central cornea or severe edema without visualization of guttata
- Dysfunctional endothelium from Pseudophakic Corneal Edema (PCE) or Iridocorneal Endothelial Syndrome (ICE) or other primary endothelial dysfunction such as Posterior Polymorphous Corneal Dystrophy (PPMD)
- Dysfunctional endothelium from prior graft failure after PKP or EK
- Controlled uveitis (defined as quiet for > 3 months off topical steroids with or without systemic immunosuppression) or no uveitis
- Controlled glaucoma with topical medications and/or prior trabeculectomy or tube shunt without ongoing hypotony (IOP < 5 mmHg) or no glaucoma
- Good candidate for corneal transplantation for either DMEK or UT-DSAEK
- Willingness and ability to undergo corneal transplantation
- Willingness to consistently use study medications (i.e. ROCK-inhibitors)
- Willingness to participate in follow-up visits
- Age greater than 18 years

DETECT II

- Dysfunctional endothelium from FECD with few guttata extending beyond 4.5 mm
- Peripheral endothelial cell count >1500 cells/mm²
- Good surgical candidate for either procedure as determined by the surgeon
- Willingness and ability to undergo corneal transplantation
- Willingness to consistently use study medications (i.e. ROCK-inhibitors)
- Willingness to participate in follow-up visits
- Age greater than 18 years

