5.2 EXCLUSION CRITERIA

An individual who meets any of the following criteria will be excluded from participation in this study:

DETECT I

- Aphakia, or anterior chamber IOL or scleral fixated IOL in study eye prior to or anticipated during EK
- Pre-operative central sub-epithelial or stromal scarring that the investigator believes is visually significant and could impact post-operative stromal clarity assessment

DETECT

Version 5.0
21 March 2023

- Peripheral anterior synechiae (iris to angle) in the angle greater than a total of three clock hours
- Visually significant optic nerve (ok to have small visual field defects) or macular severe pathology
- Inability to comply with post-operative instructions (i.e. unable to position)
- Pregnancy
- Cataract surgery within the last 3 months
- Fellow eye visual acuity <20/200

DETECT II

- Other primary endothelial dysfunction such as PPMD
- Any prior intraocular surgery other than cataract surgery
- Cataract surgery within the last 3 months
- >3 clock hours of ANY anterior or posterior synechiae
- >1 quadrant of stromal corneal vascularization
- Visually significant optic nerve or macular pathology
- Fellow eye visual acuity <20/200
- Pregnancy
- Inability to comply with post-operative instructions (i.e. unable to position)
- Hypotony (Intraocular pressure <10mmHg)
- Peripheral anterior synechiae (iris to angle) in the angle greater than a total of three clock hours
- Aphakia, or anterior chamber IOL or scleral fixated IOL in study eye prior to or anticipated during EK
- Pre-operative central sub-epithelial or stromal scarring that the investigator believes is visually significant and could impact post-operative stromal clarity assessment

5.2.1 PREGNANCY EXCLUSION:

Women of childbearing age will have to take a urine test prior to enrolling in the study. Women of childbearing age will need to use birth control while taking Ripasudil. Women will check with their doctor about what kind of birth control methods to use and how long to use them. For this study women of childbearing age would only need to use birth control for the three months of taking Ripasudil.

Pregnancy is a contraindication to Ripasudil. If participant gets pregnant during treatment with ripasudil they will need to stop taking it. Participant will continue in study but will not be on ripasudil. We will follow the patient until the end of the study.

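### Section 8.3.9 decides who gets the pregnancy test by past medical advice; section 5.2.1 sets no such limit, so a woman who could be pregnant might go untested

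*Protocol*

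**What the plan says.** Two sections of the protocol state the pregnancy safeguards.

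- **Section 5.2.1 (Pregnancy Exclusion):** "Women of childbearing age will have to take a urine test prior to enrolling in the study". It then requires birth control during the three months on ripasudil. It does not define the group. It also states: "Pregnancy is a contraindication to Ripasudil".
- **Section 8.3.9 (Reporting of Pregnancy):** the group is "Women of childbearing age (ie women who have been told by their doctors that they need to take birth control to avoid pregnancy", and these women "will be required to take a urine test prior to enrolling in the study". The birth control rule follows in nearly the same terms as in 5.2.1. The section adds: "There is no available data on the risk of taking Ripasudil during pregnancy".

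Pregnancy is listed as an exclusion for both DETECT I and DETECT II in section 5.2. The age criterion in section 5.1 is the same for both trials: "Age greater than 18 years".

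**The concern.** The procedures in the two sections are the same, but the women they apply to are not. The parenthetical in 8.3.9 is introduced as an equivalence, so it reads as a definition, and it is the only one in the protocol. It selects women by what a doctor has told them. A pre-enrolment test is there to find a pregnancy that nobody yet knows about, and past advice about contraception is a poor guide to that. A fertile woman who has never discussed contraception with a doctor, or who is trying to conceive, falls outside the definition.

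At stake is exposure to ripasudil four times a day for three months during an undetected pregnancy, in a trial that intends to prevent this. This is a participant-safety point. The primary endpoints, the sample size and the analyses are unaffected.

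**Working it through.** There is no figure to reproduce. The check is a comparison of the two sections, a search for anything else that would settle the term, and a look at how many participants it could touch.

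**1. The two rules side by side**

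| | Section 5.2.1 | Section 8.3.9 |
|---|---|---|
| Test | Urine test before enrolment | Urine test before enrolment |
| Contraception | During the three months on ripasudil | During the three months on ripasudil |
| Who | Women of childbearing age, undefined | Women of childbearing age, defined by advice from their doctors |

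**2. One woman under each rule.** Take a woman of 35 who is eligible, fertile and has never been advised to use birth control.

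- Under 5.2.1, with the term in its ordinary sense, she is tested and must use birth control while on ripasudil.
- Under 8.3.9 read literally, she is outside the defined group and is not tested. The contraception sentence in 8.3.9 uses the same term, so if the definition carries forward she is outside that rule too.

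**3. Is there a backstop elsewhere in the protocol?**

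- No other section defines the term.
- The Schedule of Activities (section 1.3) has no pregnancy-test row that would catch a woman left out.
- The exclusion for pregnancy in section 5.2 bars a woman known to be pregnant. It cannot bar one whose pregnancy is undetected; only the test can do that.
- Section 5.4 allows weeks to months between enrolment and randomization or surgery, and no later test is listed. The one pre-enrolment test therefore carries the whole burden.

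**4. Reach.** The Synopsis expects ages similar to those in the exploratory study: "the median age of study participants was 67, with an interquartile range of 64 to 71". The lower quartile is 64, so about 75% of participants would be 64 or older if those ages hold. In the baseline table reproduced in section 9.4.5, the youngest participant was 51.

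Two facts keep the reach above zero. Anyone over 18 is eligible. And the exploratory study was almost all Fuchs dystrophy (24 of 25 in each arm, 96%), whereas DETECT I also admits iridocorneal endothelial syndrome, posterior polymorphous dystrophy and prior graft failure. The protocol gives no ages for those groups, so the earlier age distribution may not carry over fully.

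The protocol does not give the number of women who could be pregnant and were never so advised. The 75% figure does not measure that group, and no count is offered.

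**The case against.** The strongest reply has four parts.

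- **The parenthetical may be lay wording only.** It does not say the advice must pre-date the study or come from outside it, so counselling by the study ophthalmologist could satisfy it. This does not rescue the text. The instruction in the protocol to use birth control is addressed to women already classed as of childbearing age, so using that counselling to decide who belongs to the class is circular.
- **Eligibility is governed by section 5, and 5.2.1 is unqualified.** A site would have to let a reporting section narrow an eligibility section. Many sites would not. But the protocol does not say which section governs, and a site looking for a definition will find only the one in 8.3.9.
- **The harm is limited.** Section 8.3.9 notes that little of a topical drop is absorbed systemically. Both sections stop the drug if pregnancy occurs. Half of DETECT I and the DMEK arm of DETECT II receive placebo in place of ripasudil. All of this stands and lowers the risk. The stop rule, however, helps only once the pregnancy is known.
- **Other documents may settle the term.** The manual of procedures and the consent forms were not available for this review and could define the group properly. That is possible. It would reduce the practical effect but leave the protocol with two different statements of the same rule.

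What remains is that few women, if any, would be affected.

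**Conclusion.** The inconsistency is real. Section 8.3.9 limits the test by medical advice and section 5.2.1 does not, and the limited version selects on the wrong characteristic. A site following 8.3.9 literally could leave untested a woman who could be pregnant.

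The point is minor. The outcome is possible, not shown, and it depends on a site applying the parenthetical as written and on such a woman presenting. With expected ages centred on 67 this should be rare. No efficacy result or sample size depends on it. It is worth correcting because the protocol itself chose to exclude pregnancy and to test for it, and because the correction is nearly free.

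**What to change.** Delete the parenthetical in section 8.3.9 and use one definition in both 5.2.1 and 8.3.9, based on whether pregnancy is biologically possible (for example, neither postmenopausal nor surgically sterile) and not on advice received. The sponsor's clinicians should set the exact wording. Adding the urine test as a row in the Schedule of Activities would make the requirement visible to sites.

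The cost is a text edit in two sections, one table row if wanted, and possibly a few more urine tests of a kind already planned.

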8.4 UNANTICIPATED PROBLEMS

8.4.1 DEFINITION OF UNANTICIPATED PROBLEMS (UP)

The Office for Human Research Protections (OHRP) considers unanticipated problems involving risks to participants or others to include, in general, any incident, experience, or outcome that meets **all** of the following criteria:

- Unexpected in terms of nature, severity, or frequency given (a) the research procedures that are described in the protocol-related documents, such as the Institutional Review Board (IRB)-approved research protocol and informed consent document; and (b) the characteristics of the participant population being studied;
- Related or possibly related to participation in the research (“possibly related” means there is a reasonable possibility that the incident, experience, or outcome may have been caused by the procedures involved in the research); and
- Suggests that the research places participants or others at a greater risk of harm (including physical, psychological, economic, or social harm) than was previously known or recognized.

8.4.2 UNANTICIPATED PROBLEM REPORTING

The site investigator will concurrently report unanticipated problems (UPs) to the Medical Monitor and the Lead PI/Clinical Coordinating Center for submission to WCG IRB. The UP report will include the following information:

- Protocol identifying information: protocol title and number, PI’s name, and the IRB project number;
- A detailed description of the event, incident, experience, or outcome;
- An explanation of the basis for determining that the event, incident, experience, or outcome represents an UP;
- A description of any changes to the protocol or other corrective actions that have been taken or are proposed in response to the UP.

To satisfy the requirement for prompt reporting, UPs will be reported using the following timeline:

- Any deaths related to the study intervention must be reported by the site investigator to the Medical Monitor and the Lead PI/Clinical Coordinating Center for submission to WCG IRB within 1 business day of the investigator becoming aware of the death.
- UPs will be reported to the Medical Monitor and the Lead PI/Clinical Coordinating Center for submission to WCG IRB within 5 days of the investigator becoming aware of the event.
- All UPs should be reported to appropriate institutional officials (as required by an institution’s written reporting procedures), the supporting agency head (or designee), and the Office for Human Research Protections (OHRP) within 30 days of WCG IRB’s receipt of the report of the problem from the lead investigator.

8.4.3 REPORTING UNANTICIPATED PROBLEMS TO PARTICIPANTS

Participants will be notified of UPs in aggregate. When UPs affect an individual, they will be notified individually by the masked treating physician.

DETECT

Version 5.0
21 March 2023

8.4.4 NONCOMPLIANCE

The site investigator will concurrently report instances of Non-Compliance to the Study Chair/Clinical Coordinating Center for submission to WCG IRB.

It is the responsibility of investigators and research staff to follow the written protocol approved by the IRB. When investigators and/or research staff do not follow the written protocol it will require reporting to the Study Chair/Clinical Coordinating Center and the Lead IRB if it meets one or more of the categories below:

- 1) Report within 5 days: Violations (failure to follow the protocol) that harmed, or **could have** harmed, participants/subjects or others or that indicate increased risk of harm;
- 2) Report within 5 days: Deviations committed to eliminate an immediate hazard for a participant/subject; or
- 3) Report at Continuing Review or Next Report: Other researcher failure (due to the action or inaction of the investigator or research staff) to follow the protocol that do not impact subject safety, participant's rights, or the completeness, accuracy and reliability of study data

Promptly reportable events include:

Report within one business day:

- **Unexpected Death:** Unexpected death of a locally enrolled participant/subject who has not withdrawn from the research when the death is unanticipated and possibly related to the research.
- **Breach of Confidentiality:** Any instance where records of research participants were improperly disclosed or shared.

Report within 5 business days:

- **Increase in Risk:** Information that indicates a new or increased risk, or a safety issue. For example: New information (e.g., an interim analysis, safety monitoring report, publication in the literature, sponsor summary report, or investigator finding) indicates an increase in the frequency or magnitude of a previously known risk, or uncovers a new risk. An adverse event that indicates a potential increase in risk or reduction in benefit (such as those that may prompt a change to the protocol or consent form).
- Withdrawal, restriction, or modification of a marketed approval of a drug, device, or biologic used in a research protocol.
- Protocol violation that harmed or could have harmed subjects or others or that indicates participants/subjects or others might be at increased risk of harm.
- Complaint of a participant/subject that indicates participants/subjects or others might be at increased risk of harm or at risk of a new harm.
- Any changes significantly affecting the conduct of the research.
- Harm: Any harm experienced by a participant/subject or other individual that, in the opinion of the investigator, is unexpected and at least probably related to the research procedures.
 - A harm is "unexpected" when its specificity or severity is inconsistent with risk information previously reviewed and approved by the IRB in terms of nature, severity, frequency, and characteristics of the study population.
 - A harm is "probably related" to the research procedures if, in the opinion of the investigator, the research procedures more likely than not caused the harm.
- Non-compliance: Allegation of investigator or study team noncompliance or finding of investigator or study team noncompliance.
- Audit: Audit, inspection, or inquiry by a federal agency (e.g. FDA Form 483).
- Report: Data safety monitoring reports from councils, committees, or boards charged with data and safety oversight activities; or other reports such as FDA non-approval letters.

DETECT

Version 5.0
21 March 2023

- Researcher error: Failure to follow the protocol due to the action or inaction of the investigator or research staff.
- Confidentiality: Unauthorized disclosure of confidential information.
- Protocol Deviation: Change to the protocol taken without prior IRB review to eliminate an apparent immediate hazard to a subject.
- Incarceration: Incarceration of a subject in a study not approved by the IRB to involve prisoners.
- Complaint: Unresolved subject complaint.
- Suspension: Suspension or premature termination by the sponsor, investigator, institution or other IRB.
- Disqualification / Termination: Change in qualification of any member of the study team based on state medical board, hospital medical staff action, or other disqualification by professional board or employer.

